MRI may be superior to CT for detection of liver metastases in pancreatic cancer [9]. As liver metastases from resectable pancreatic cancer tend to be small [10], for which MRI (with use of diffusion weighted imaging and liver-specific contrast) has a high sensitivity, routine use of preoperative MRI could be beneficial. However, the feasibility of using MRI in detection of liver metastases in pancreatic cancer patients has been sparsely investigated. One prospective study of 69 pancreatic cancer patients found that almost 25% had liver metastases on MRI that were not visible on CT [11], whereas a retrospective study of 216 patients found that MRI revealed liver metastases in only 5% of patients with CT-assessed non-metastatic pancreatic cancer [12]. The latter study also found a longer time to recurrence after surgery in patients undergoing preoperative MRI, suggesting that preoperative MRI may be beneficial in pancreatic cancer patients. However, they did not provide information on why MRI was performed, and findings are unlikely to be generalizable. Furthermore, only few studies have examined the use of MRI in assessing the local extent of the tumor, suggesting it is not inferior to CT [13, 14].

Thus, MRI may provide a superior alternative to conventional CT in order to improve treatment allocation for pancreatic cancer patients. However, there is a substantial need for high-

quality research to examine this. Specifically, no randomized clinical trial (RCT) has been conducted.

PURPOSE AND OVERALL AIM

[figure not shown]
We propose to conduct a nationwide RCT to examine the feasibility of using MRI for tumor staging and identification of liver metastases in pancreatic cancer patients. *The aim is to improve selection of pancreatic cancer patients for surgery in order to increase overall survival*. Within this RCT, we will conduct three studies outlined below.

STUDY POPULATION AND DESIGN

Patients

200 patients with CT-assessed resectable pancreatic cancer allocated to surgery by the local multidisciplinary tumor board (MDT) will be included. Patients will be randomized to either the intervention (preoperative MRI, n=100) or control/standard-of-care (no preoperative MRI, n=100) arm.

Study design and patient flow

An overview of the proposed study design is shown in Figure 1.

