Upon consent, patients will be electronically randomized to one of the two treatment arms. Patients in the control arm will proceed directly to surgery. Patients in the intervention arm will have an MRI performed after randomization and before treatment. If the interval from CT to MRI is >14 days, a new CT will be performed to assure a valid comparator. The MRI will be read by an experienced gastro-radiologists blinded to the patient's identity and initial CT scan. Based on the MRI, the treatment decision will be made (*Figure 2*):

Figure 1. Study design. R: Randomization.

- 1) No liver metastases on MRI (expected ~75%): Surgery as planned.
- 2) Non-specific liver lesions on MRI, not seen on CT (expected $\sim 10\%$): Surgery as planned.
- 3) Liver metastases on MRI (expected ~15%): Referral to liver biopsy and oncological treatment if malignancy is verified. If biopsy is inconclusive, repeat liver MRI after one month.

[figure not shown]

Figure 2. Patient flow in the intervention arm. MDT: Multidisciplinary team conference.

Follow-up

Patients will be followed for up to three years for information on treatment, recurrence, and vital status. We will conduct standard-of-care follow-up CT at 3, 6, 9, 12, 18, 24, 30, and 36 months postoperatively in all patients. Primary end-point for this project will be one-year survival. For subsequent studies, we will also perform analyses of three-year survival.

SPECIFIC STUDY AIMS, HYPOTHESES AND OUTCOMES

Study I: To compare tumor staging of pancreatic cancer patients assessed by MRI versus upper abdominal CT.

Study II: To assess the ability of MRI to detect liver metastases in pancreatic cancer patients with resectable tumor on CT.

Study III: To assess the impact of MRI on treatment allocation, recurrence, and survival in pancreatic cancer patients with a resectable tumor on CT.

Details of study hypotheses, population, and analytical plans are outlined in Figure 3.

	Study I	Study II	Study III
Aim	To compare tumor	To assess the ability of	To assess the impact of
	staging of pancreatic	MRI to detect liver	MRI on treatment
	cancer patients assessed	metastases in pancreatic	allocation, recurrence,
	by MRI versus upper	cancer patients with	and survival in pancreatic
	abdominal CT	resectable tumor on CT	cancer patients with a
			resectable tumor on CT
Hypothesis	MRI is non-inferior to CT	MRI will detect liver	Use of MRI will change
	with respect to tumor	metastases in patients	treatment allocation and

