	staging	with a resectable tumor	improve overall survival
		on CT	
Population	Patients in the	Patients in the	Patients in both arms
	intervention arm (N=100)	intervention arm (N=100)	(N=200)
Analysis	Agreement assessed by	Agreement assessed by	Treatment allocation and
	intraclass correlation	intraclass correlation	recurrence by Chi ² test
	coefficient (ICC)	coefficient (ICC)	Survival analyses by
			Kaplan-Meier estimation

Figure 3. Outline of the three studies.

POWER CALCULATIONS AND FEASIBILITY

Assuming alpha=0.05, power of 80%, and a hazard ratio of death of 1.5, we need 191 patients in total. To guard against dropout of 5%, we aim to include 200 patients. On average, all four institutions performing pancreatic cancer surgery in Denmark (Rigshospitalet, Aarhus, Aalborg, and Odense) shall include 50 patients. We aim to finalize patient enrollment during the first 18 months of the study period, equaling to 2.8 patients monthly in each institution. In total, ~300 resections will be performed during this 18-month period. We consider it feasible and realistic to include two-thirds of these patients.

IMAGING PROTOCOLS

CT imaging protocol

As a part of the routinely workup for staging pancreatic cancer, all patients referred to the local hepato-pancreato-biliary MDT board undergo a pancreas-specific CT scan. All CT scans include a

portal venous phase (PVP) of the liver. CT scanners from different vendors will be used to acquire the images. The PVP will routinely obtained by 120 KV and mAs range from 150 to 290 depending of the body mass of the patient and the scan system. Contrast medium will be administered intravenously as a bolus injection by weight bases contrast Iodine concentration of 500 – 750 mg I/kg and a rate of 3-5 ml/s, followed by a saline flush of 20–40 ml. The scan delay for the PVP will be 50 sec (post-threshold, bolus tracking). Axial slice thickness of 2 mm slices will be reconstructed with 1 mm increments.

MR imaging protocol

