The MRI will be performed using 1.5 or 3.0 T MR scanners of different vendors. The liver will be scanned using axial and coronal T2W single shot (SS) TSE, axial DWI (minimum b-values of 50 and 800) and axial T1W 3D spoiled gradient echo for gadoxetic acid (Primovist, Bayer Pharma, Berlin, Germany) contrast scans. Both a dynamic contrast scan consisted of; pre-contrast phase, arterial phase (timed using bolus tracking) followed immediately by porto-venous phase; late phase at 2 min and hepato-biliary phase 15 min after contrast injection. The gadoxetic acid contrast will be injected at 1 or 2 mL/s depending of using a dilution 1:1 of gadoxetic acid and saline 9mg/ml or not. The dose will be 0.025 mmol/kg body weight with a maximum of 2.5 mmol using a power injector.

Analysis for metastatic lesions

Each modality will be read anonymized. Both CT and MRI images will be read independently by dedicated radiologist from each participating site as part of the routine work-up in staging pancreatic cancer. The CT scan will be performed as the first examination followed by MRI scan within 14 days after the CT scanning. For all focal hepatic lesions confidence of malignancy will be categorized via a 3-point scale, 1: benign, 2: indeterminate, 3: malignant.

FEASIBILITY

Time schedule

The project will begin in January 2022 and end in December 2024. We will include the patients within the first 18 months of the project period. In the final year of the study period, we will perform data analyses and writing of scientific papers. This will allow for a sufficient follow-up period of all patients (please see *Figure 4* for detailed time schedule).

[figure not shown]

Figure 4. Time schedule.

Scientific and non-scientific personnel

At each institution, one research nurse will be responsible for identification of potential study subjects and, in collaboration with the surgeon, perform the practical work on obtaining informed consent and randomize the patients. The research nurse will also be responsible for each patient's path through the project, *e.g.* schedule the imaging and collect data, and to coordinate the project with the research nurses at the other participating sites.

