Beside the salary for [name] and two research nurses mentioned above, we apply the Danish Cancer Society for expenses related to MRI scans. The departments will hold expenses for CT scans for the 50% of the patients that are expected to have more than 14 days between CT and MRI. Please see the attached budget for more details.

FUTURE PERSPECTIVES

We expect this project to substantially improve our ability to tailor the optimal treatment for each individual with pancreatic cancer. Underdiagnosis of liver metastases delays the initiation of life-prolonging chemotherapy. Thus, with proper preoperative detection of liver metastases, our project will improve both survival and quality-of-life, as patients will be spared from unnecessary major surgery. Thus, findings from our project is expected to have an immediate clinical impact. Furthermore, if MRI is non-inferior to CT with respect to tumor staging, it may replace CT in the diagnostic workup of pancreatic cancer patients.

ETHICAL CONSIDERATIONS

This project will be conducted according to the Helsinki Declaration. The project needs to be registered at the Danish Data Protection Agency in accordance with the Central Denmark Region common registration system and it also requires approval from the Central Denmark Region Ethics Committee. We will ensure that all permissions are granted when study starts. All information involving patients will be handled according to national law on personal data information. Both positive, negative, and inconclusive results will be published, and presented at scientific meetings. Results will be presented at international scientific congresses, and we will aim for publications in

high-impact journals with focus on oncology, radiology, and surgery. The study will be registered at ClinicalTrials.gov and monitored by the Good Clinical Practice Unit at Aarhus University Hospital.

REFERENCES

- Gillen S, Schuster T, Meyer Zum Buschenfelde C, Friess H, Kleeff J.
 Preoperative/neoadjuvant therapy in pancreatic cancer: a systematic review and metaanalysis of response and resection percentages. PLoS Med. 2010;7: e1000267.

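### Study I states a non-inferiority hypothesis for tumor staging, but its only analysis is an ICC, which has no direction and comes with no rule for concluding non-inferiority

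*Combined protocol and SAP*

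**What the plan says.** The section on specific study aims refers to Figure 3 for hypotheses, populations and analytical plans. For Study I, Figure 3 gives:

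- **Hypothesis:** "MRI is non-inferior to CT" with respect to tumor staging.
- **Population:** the intervention arm, N=100.
- **Analysis:** "Agreement assessed by" the ICC. Nothing else is listed.

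The staging variable is not named. The Background says that a few studies have looked at MRI for "assessing the local extent of the tumor, suggesting it is not inferior to CT", which points to local stage. The only reading scale defined, under Analysis for metastatic lesions, concerns the liver: "For all focal hepatic lesions confidence of malignancy will be categorized via a 3-point scale".

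Future Perspectives says what would follow: "if MRI is non-inferior to CT with respect to tumor staging, it may replace CT in the diagnostic workup of pancreatic cancer patients". The Patients section restricts entry to tumors that CT shows as resectable and that the tumor board has allocated to surgery. The one power calculation is for the hazard ratio of death.

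**The concern.** Non-inferiority is a directional claim: MRI is not worse than CT by more than a stated amount. It needs a measure of worse (accuracy against a reference stage, for example) and a margin. An ICC between the two modalities measures how alike they are. An absolute-agreement ICC falls if one modality stages systematically higher, but it still does not show which one is right.

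So the plan can be followed exactly without testing its own hypothesis. At moderate agreement the result cannot be read against that hypothesis. At high agreement there is no rule set in advance for calling MRI non-inferior, so the call would be made after seeing the data. Future Perspectives makes possible replacement of CT conditional on that call.

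**Working it through.** **The plan's own figure.** None is given for Study I. The stated 191 belongs to the survival comparison. Schoenfeld's formula for the number of deaths (two-sided alpha 0.05, 80% power, hazard ratio 1.5, 1:1) gives 4 × (1.960 + 0.842)² / (ln 1.5)² = 191. It plays no part below.

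**Step 1: the ICC has no direction.** Take 100 constructed pairs and a two-level stage, truth split 50/50. One modality is always right; the other is wrong in 10 patients at each level. Eighty pairs agree and 20 disagree.

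- Between-patient sum of squares: 2 × 80 × 0.5² = 40. Residual: 20 × 0.5 = 10. Each has 99 degrees of freedom, and the modality means are equal.
- Consistency ICC = (40 − 10)/(40 + 10) = 0.600.
- Absolute-agreement ICC = (MSR − MSE)/(MSR + MSE + 2(MSC − MSE)/100), with MSR = 40/99, MSE = 10/99 and MSC = 0. This is 0.3030/0.5030 = 0.602.

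CT 100% and MRI 80% accurate gives these values. CT 80% and MRI 100% accurate gives the same ones.

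**Step 2: what agreement does bound.** Patients staged the same by both modalities are both right or both wrong, so they add nothing to the accuracy difference. Hence

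|accuracy of MRI − accuracy of CT| ≤ proportion staged differently.

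If 5 of 100 are staged differently, MRI is at most 5 points worse in the sample (Clopper-Pearson 95% CI for the proportion 1.6–11.3%). If 20 of 100 are, the limit is 20 points (12.7–29.2%).

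**Step 3: the ICC does not supply that proportion.** Simulation: absolute-agreement ICC, n=100, 4,000 runs per scenario, three-level stage, errors to an adjacent category, all errors in one modality. Splits and error rates are assumptions; the documents give neither.

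| Assumed true stage split | ICC, 5% staged differently | ICC, 20% staged differently |
|---|---|---|
| 20/50/30 | about 0.95 | about 0.80 |
| 10/80/10 | about 0.88 | about 0.61 |
| 5/90/5 | about 0.78 | about 0.44 |

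An ICC near 0.8 can therefore go with 5% or with 20% staged differently. At 20/50/30 it also arises whether MRI is 20 points less accurate, equally accurate (10% errors each) or 20 points more accurate (0.79, 0.81 and 0.80).

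**Step 4: restricted range.** All patients are CT-resectable, so CT stage may vary little. In the limit CT stage is constant. With S the sum of squared deviations of the MRI values from their mean, the between-patient and residual sums of squares are then both S/2, so MSR = MSE and the ICC is 0. That holds whether MRI differs in 5 or in 20 of 100 patients.

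**Step 5: could non-inferiority be tested instead?** Assume a reference stage from surgery or pathology, equal true accuracy, an illustrative 10-point margin and one-sided alpha 0.025. Discordance here is the share of patients in whom exactly one modality is right.

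SE = √(discordance/n); power = Φ(0.10/SE − 1.96).

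For n, take 100 less 5%, 15% or 25%: 95, 85 or 75. These shares are the MRI-positive figures in the Background (5%, almost 25%) and the patient flow (about 15%), used as a stand-in for patients not operated on. Not all of those patients need be diverted from surgery. Example: n=85 and 10% discordance give SE = √(0.10/85) = 0.0343 and power = Φ(2.915 − 1.96) = 83%.

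| Discordance | n=95 | n=85 | n=75 |
|---|---|---|---|
| 5% | 99% | 98% | 97% |
| 10% | 87% | 83% | 78% |
| 15% | 71% | 66% | 61% |
| 20% | 59% | 54% | 49% |
| 30% | 43% | 39% | 35% |

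**The case against.** The best defence is that CT is the accepted standard, so high agreement with it is itself evidence that MRI is not much worse. This stands in part. Step 2 shows that agreement bounds the deficit, so a reader who inferred that agreement data say nothing about non-inferiority would go too far. But the bound comes from the proportion staged differently, which the plan does not report, and nothing says how small it must be.

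Three other strong readings are tempting and not supported:

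- **That a given ICC implies a given possible deficit**, such as 20 points at 0.80. This holds only under the assumed 20/50/30 split, and the documents give no stage mix.
- **That a proper non-inferiority test would be hopelessly underpowered, so the hypothesis has to go.** The documents give no discordance figure, and the table in step 5 runs from 35% to 99%.
- **That the trial's main result is at risk.** Study I is supporting, and the primary endpoint is one-year survival.

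It can also be said that the sentence on replacing CT is an aspiration under Future Perspectives, phrased as a possibility. That is fair and limits the weight of the point. It does not supply the missing rule.

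One passage was removed before review and some figures are not shown, so statements of absence apply to the supplied text. Figure 3, which the protocol names as the outline of the analytical plans, is present as text.

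**Conclusion.** The point holds. The Study I hypothesis and its analysis do not match: the first is directional, the second is symmetric, and no margin, threshold, reference standard or staging variable connects them. The symmetry is exact and needs no assumption. The size of the problem in practice depends on the unknown stage mix and disagreement rate. Under the assumed splits, the same 5% staged differently gives an ICC from about 0.95 down to about 0.78, and zero if CT stage does not vary. In a CT-resectable population a low ICC could therefore sit beside near-complete agreement.

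This should be corrected before analysis. It affects what Study I may claim, not the survival comparison.

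**What to change.** 1. Name the staging variable and its scale.
2. Restate the hypothesis as an aim: *to estimate agreement between MRI and CT in tumor staging*. Delete the non-inferiority wording.
3. Make the CT-by-MRI cross-table the main result, with the proportion staged differently overall and in each direction (MRI higher, MRI lower), each with a 95% CI. This describes stage shifts and bounds the accuracy difference; it does not show which modality is right.
4. Report the ICC with its 95% CI as secondary, with a caution about restricted range.
5. Limit the sentence in Future Perspectives to agreement in CT-resectable patients.

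The cost is wording and one table. Study I already needs a CT stage and an MRI stage for each patient, so no new data are required. The downside is that the non-inferiority claim is given up.

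The alternative, if the sponsor wishes to keep non-inferiority, is to test the paired accuracy difference (MRI minus CT) against surgical or pathological stage in operated patients. The margin must be justified clinically and fixed in advance, and power stated for a plausible range of discordance. This assumes that such stage data are available from routine records; the supplied text does not list them. The result would apply only to patients operated on after both scans.

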MAGIPAC trial: Magnetic Resonance Imaging for Better Selection of Pancreatic Cancer Patients for Surgery: A Randomized Clinical Trial.

BACKGROUND AND SIGNIFICANCE

Pancreatic cancer has a dismal prognosis with a 5-year survival of only 8% [1]. Despite surgery being the only chance for cure, only 20% of the patients are eligible for surgical treatment, as most have metastatic disease at diagnosis [2]. Pancreatic cancer surgery is a major procedure with a substantial morbidity and mortality [3]. Therefore, it is important to avoid futile resections that will delay initiation of life-prolonging chemotherapy in patients who will not benefit from surgery. Whether the patient can be operated depends on the local extent of the tumor and the presence of distant metastases (most often in the liver), which are contraindications to surgery [4-6].

Currently, computed tomography (CT) is state-of-the-art for assessing pancreatic cancer resectability [7]. However, CT has some shortcomings. Although it performs well in assessing the local extent of the tumor, it has limited sensitivity for detecting small liver metastases in pancreatic cancer [8]. Relying solely on CT imaging therefore leads to futile resections in patients with undetected liver metastases. This will impair survival, as patients will have to recover from surgery and the associated complications before they can initiate chemotherapy. These shortcomings may be overcome by using liver and pancreatic magnetic resonance imaging (MRI) instead of CT.

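### Study II asks whether MRI detects liver metastases, but its only stated analysis is an agreement coefficient, which does not estimate detection

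*Combined protocol and SAP*

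**What the plan says.** The aims section reads "Study II: To assess the ability of MRI to detect liver metastases in pancreatic cancer patients with resectable tumor on CT". The Figure 3 hypothesis is that MRI will find such metastases. The population is the intervention arm, N=100. The Study II analysis cell names only agreement by "intraclass correlation" coefficient, with the same wording as Study I. It does not give the pair of reads, the unit (patient or lesion), the ICC form or a target value.

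Other parts of the plan bear on this:

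- **Comparator.** Under Study design and patient flow, if more than 14 days separate CT and MRI, "a new CT will be performed to assure a valid comparator". The budget text expects this interval to be exceeded in 50% of patients.
- **Verification.** The same section has "Liver metastases on MRI (expected ~15%): Referral to liver biopsy and oncological treatment if malignancy is verified", and then "If biopsy is inconclusive, repeat liver MRI after one month". The other two MRI groups (about 75% and about 10%) go to surgery, with no biopsy stated.
- **Rating.** Analysis for metastatic lesions sets a 3-point scale for each focal liver lesion (benign, indeterminate, malignant) but names no estimator.
- **Rationale.** The Background argues from yield. In one cited study "almost 25% had liver metastases on MRI that were not visible on CT"; in another "MRI revealed liver metastases in only 5% of patients with CT-assessed non-metastatic pancreatic cancer".

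**The concern.** The hypothesis is about how often MRI finds metastases that CT did not. An ICC describes how alike two sets of ratings are. In this population a useful MRI is one that disagrees with CT, so a low CT-MRI ICC is compatible with success, with false alarms, or with almost no findings. Study II as planned could then report its one analysis and still leave its hypothesis neither supported nor refuted. If yield were reported anyway, several choices would be made after the data were seen: the denominator, which CT counts, how inconclusive biopsies are handled, and how lesions indeterminate on CT are treated.

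**Working it through.** **The plan's own figure.** There is none for Study II. The 191 patients under Power Calculations come from a hazard ratio for death and concern survival in Study III.

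**Which pair of reads?**

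- CT versus MRI is the natural reading, because the patient-flow text treats CT as the comparator.
- Inter-reader agreement would measure reproducibility, not detection.
- MRI versus biopsy would not work either. Only MRI-positive patients are referred to biopsy, so the MRI rating does not vary among them.

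**Why CT varies little.** The Background lists "the presence of distant metastases (most often in the liver), which are contraindications to surgery", and everyone enrolled has been allocated to surgery on CT.

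**Inputs.** N=100 (Figure 3). MRI-indeterminate 10 (the expected ~10%). MRI-malignant m = 5, 15 or 25 (the two cited yields and the expected ~15%). The remaining 90 − m are benign. Ratings are 1/2/3 per patient. Taking the patient as unit is an assumption, because the scale is defined per lesion and no rule pairs an MRI-only lesion with a CT rating.

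**Formula.** With two reads and n patients, let MSR, MSC and MSE be the between-patient, between-modality and residual mean squares:

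ICC(2,1) = (MSR − MSE) / [MSR + MSE + 2(MSC − MSE)/n]

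For two reads, MSR − MSE = 2·cov(CT, MRI). If CT is constant the covariance is zero, so the ICC is zero whatever MRI shows.

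**Case 1: CT rated benign in all 100**

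| MRI malignant | MSR | MSE | ICC(2,1) | Yield, exact 95% CI |
|---|---|---|---|---|
| 5 | 0.131 | 0.131 | 0.00 | 5% (1.6 to 11.3) |
| 15 | 0.273 | 0.273 | 0.00 | 15% (8.6 to 23.5) |
| 25 | 0.374 | 0.374 | 0.00 | 25% (16.9 to 34.7) |

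The consistency form ICC(3,1) is also 0.00. The one-way form is −0.07, −0.12 and −0.19.

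**Case 2: repeat CT also rates c of the 15 MRI-malignant patients as malignant (c assumed)**

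| c | MSR | MSE | MSC | ICC(2,1) | Found by MRI only |
|---|---|---|---|---|---|
| 1 | 0.325 | 0.260 | 7.22 | 0.09 | 14 |
| 3 | 0.429 | 0.235 | 5.78 | 0.25 | 12 |
| 5 | 0.530 | 0.207 | 4.50 | 0.39 | 10 |

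For c = 3: (0.4285 − 0.2345) / [0.4285 + 0.2345 + 2(5.78 − 0.2345)/100] = 0.1940/0.7739 = 0.25. At a fixed MRI yield the ICC rises as MRI adds less over CT.

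**Case 3: ten CT-indeterminate patients (assumed), MRI yield 15.** ICC(2,1) is 0.45, 0.17 or −0.11 according to whether those ten are MRI-malignant, MRI-indeterminate or MRI-benign. The MRI yield is 15% in all three.

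**Biopsy.** The result is not an input to a CT-MRI ICC. With 15 MRI-positives, the ICC is the same whether 0, 12 or 15 are verified. Verified yield is then 0% (0 to 3.6), 12% (6.4 to 20.0) or 15% (8.6 to 23.5).

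**The case against.** The best defence is that Figure 3 is an outline. The patient flow already sorts MRI results into three groups, so a yield table is easy to produce. Verified metastases redirect treatment and so also enter Study III's Chi-square test of treatment allocation. This limits the harm, but it does not supply the missing analysis. The plan refers the reader to Figure 3 for its analyses, no other section adds a detection estimate, and a between-arm test of allocation does not estimate verified yield.

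Three stronger readings are tempting and are not supported:

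- **The ICC must come out at zero.** This holds for a two-way ICC if the patient-level CT rating is constant. Selection makes low variation likely, but no section states a constant rating. The scale has an indeterminate category, and a repeat CT may show new lesions. The non-zero values above rest on assumed counts and placements, and no lesion-level ICC was computed.
- **The plan expressly leaves biopsy out of Study II.** The pair of reads is not named, so this is an inference from the CT-MRI reading. Nor is the insensitivity to biopsy peculiar to the ICC: any CT-MRI statistic, including a cross-table, shares it.
- **The trial cannot answer the question, or its main result is compromised.** The planned scans and biopsies allow yield to be estimated, and the one-year survival end-point does not depend on this analysis.

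**Conclusion.** The concern stands as a mismatch between aim and named method in one of the three component studies. Its importance is moderate: it should be fixed, but it does not threaten the primary end-point. On the CT-MRI reading, the ICC cannot tell a 5% from a 25% yield if CT is constant. If CT varies, the coefficient depends on the few patients with a non-benign CT rating and, at fixed MRI yield, increases as CT finds more of the same disease. The other two candidate pairs would not estimate detection either. The numerical results assume patient-level ratings, all 100 patients scanned and 10 MRI-indeterminate patients. The conclusion that an ICC does not estimate detection needs none of these.

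**What to change.** Replace the ICC as the main Study II analysis as follows.

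1. **Main estimate.** Among MRI-examined intervention-arm patients, the proportion with a biopsy-verified liver metastasis rated malignant on MRI and not rated malignant on the comparator CT (the repeat CT where done). Use the patient as unit and an exact 95% CI. Report how many were randomised but not scanned.
2. **Inconclusive biopsies.** Count MRI-positive patients without a conclusive biopsy as not verified in the main estimate and as verified in a bounding analysis. Illustration with 100 scanned, 12 verified, 2 inconclusive and 1 benign: 12% (6.4 to 20.0); upper case 14/100 = 14% (7.9 to 22.4).
3. **CT status.** Classify each patient once by the CT status of the verified lesion (not seen or benign, versus indeterminate), with a stated rule for patients who have both.
4. **PPV.** Report the PPV of an MRI malignant rating among patients with a conclusive biopsy, with an exact CI. In the same illustration, 12/13 = 92% (64.0 to 99.8).
5. **Descriptive items and limits.** Keep the CT-MRI cross-table as description. State that yield and PPV do not measure metastases missed by MRI, because MRI-negative patients are not biopsied. Early liver recurrence on the already scheduled follow-up CTs can be reported descriptively.

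The cost is analysis wording and a little more tabulation, with no new scans, biopsies or patients. The drawback is a wide PPV interval from about 15 biopsies.
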